Anyone transitioned from warfarin to an oral anticoagulant prior to the first dose of lerapolturev should have an INR < 1.5x upper limit of normal in order to participate. Antiplatelet agents (eg, aspirin, clopidogrel, etc.) are not considered anticoagulants for the purposes of this study (ie, are allowed) 21. A pregnant or nursing female, or women of child-bearing potential and men who are sexually active and not willing/able to use medically acceptable forms of contraception starting from signed ICF through 150 days after last anti-PD-1 dose 22. History of human serum albumin allergy 23. History of neurological complications due to polio virus infection 24. History of agammaglobulinemia 25. Concurrent participation in a separate interventional clinical trial during this study 26. Any underlying medical condition for which, in the opinion of the investigator, participation would not be in the best interest of the participant (eg, compromises the participant's wellbeing) or that could prevent, limit, or confound protocolspecified assessments Concomitant Pembrolizumab or nivolumab (Arm 2 only) **Treatment** Lerapolturev (formerly PVSRIPO): Oncolytic Polio/Rhinovirus Investigational Recombinant **Drugs** Up to approximately 30 sites Planned Study Sites Criteria for Efficacy: Changes in skin lesion and/or radiographic tumor measurements and survival will be assessed per RECIST 1.1 at Assessments regular intervals to evaluate efficacy: participants achieving objective response (along with associated durations) or disease control by Week 26 or upon anti-PD-1 re-challenge (Arm 1 and safety run-in participants that crossover to Arm 2, analyzed from time of crossover but separately from Arm 2) through study completion. Assessment of anti-tumor response by iRECIST will be exploratory. **Safety:** Laboratory and spontaneously reported AEs, to evaluate safety and tolerability to determine incidence and severity of treatment-emergent AEs for duration of the study

Confidential Page 17 of 109

	Biomarkers: Biological samples will be collected as indicated in the schedule of assessments (SOA) to evaluate immune, genetic, or cytologic factors impacting lerapolturev mechanism of action (MOA), anti-tumor response, and/or to evaluate immune-related AEs

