2 OBJECTIVES AND ENDPOINTS

2.1 Objectives and Endpoints

Objectives	Endpoints/Evaluation Criteria			
Primary				
To evaluate the anti- tumor activity of lerapolturev with and without anti-PD-1, in participants who have failed anti-PD-1/L1- based therapy	Overall Response Rate (ORR): the proportion of participants achieving confirmed complete (CR) or partial response (PR), per RECIST 1.1 criteria.			
To evaluate the safety/tolerability of lerapolturev with and without anti-PD-1, in participants who have failed anti-PD-1/L1-based therapy To evaluate the effect of	 The frequency and severity of treatment-emergent adverse events (AE) via Common Terminology Criteria for Adverse Events (CTCAE, v5.0) Changes in laboratory (hematology, chemistry) and vital sign parameters Lerapolturev AESIs Anti-PD-1 irAEs Study treatment discontinuation due to AEs Changes from baseline in the number of CD8+ tumor 			
lerapolturev on the TME of injected and non-injected lesions when administered with and without anti-PD-1 therapy	 Changes from baseline in the number of CD8+ tumor infiltrating lymphocytes (TILs) Changes from baseline in PD-L1 expression 			
Secondary To evaluate summivel and	O			
To evaluate survival and disease control outcomes of lerapolturev with and without anti-PD-1, in participants who have failed anti-PD-1/L1-based therapy	 Overall survival (OS): time from treatment group assignment until death from any cause Duration of Response (DOR): time from confirmed objective response (CR or PR per RECIST 1.1) until unequivocal disease progression or death, whichever occurs first Disease control rate (DCR): the proportion of participants achieving confirmed CR, confirmed PR, or stable disease (SD) per RECIST 1.1, as best response Disease control rate-6months (DCR-6mo): the proportion of participants achieving confirmed CR (any duration), confirmed PR (any duration), or SD (≥ 6 months) per RECIST 1.1 as best response Durable Response Rate (DRR): the proportion of participants with confirmed CR or PR (per RECIST 1.1) lasting at least 6 months 			

Confidential Page 48 of 109

	Progression-free survival (PFS): time (number of months) from treatment group assignment until date of documented radiologic disease progression per RECIST 1.1 or death due to any cause, whichever comes first		
Exploratory:			

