3.1.1 Crossover

Participants receiving lerapolturev monotherapy (Safety Run-In Cohort or Arm 1) may crossover to combination (lerapolturev and anti-PD-1) therapy if any of the following criteria are met

- radiologic disease progression per RECIST v1.1 (progression does not need to be confirmed prior to crossover)
- have not had progression or confirmed partial response per RECIST v1.1 by week 26 on study
- o partial response ≥ 6 months in duration

All participants crossing over to combination therapy should have a complete assessment of tumor burden (ie, scans and caliper/ruler measurement of skin lesions with photographic documentation) ≤ 28 days prior to starting the combination. The dose of lerapolturev administered in combination will be the same as monotherapy and is detailed in Table 7. The schedule of lerapolturev injections at the time of initiation of combination therapy will depend on the timing of crossover (Table 6).

Confidential Page 51 of 109

Table 6. Lerapolturev Injection Schedule After Crossover

Schedule of lerapolturev monotherapy injections at the time of crossover	Timing of when criteria for crossover are met	Recommended lerapolturev dosing schedule for combination
Participant is receiving weekly injections	< 6 months from Cycle 1 Day 1	Continue weekly injections for a total of 7 (monotherapy + combination) followed by every 3 week dosing (pembrolizumab) or every 4 week dosing (nivolumab)*
Participant is receiving injections every 3 weeks (pembrolizumab) or every 4 weeks (nivolumab)	< 6 months from Cycle 1 Day 1	Continue concurrent dosing schedule
Participant is receiving injections every 3 weeks (pembrolizumab) or every 4 weeks (nivolumab)	≥ 6 months from Cycle 1 Day 1	Weekly x 7 followed by every 3 week dosing (pembrolizumab) or every 4 week dosing (nivolumab)

*NOTE: Anti-PD-1 dosing begins Day 1 of crossover. Following the 7th weekly injection, lerapolturev should be administered Q3w when in combination with pembrolizumab (given Q3 or 6w), or Q4w when in combination with nivolumab (given Q2 or 4w).

3.1.2 Considerations for Modification of Dose and/or Dosing Schedule for Participants receiving the Q3/4W Schedule of Injections.

Lerapolturev Dose: All participants receiving lerapolturev on the **Q3/4W** schedule will have their lerapolturev dose adjusted as described in Section 5.3.

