8.5.1 Efficacy Analyses

The primary endpoint for measuring anti-tumor activity will be ORR, which will be evaluated once participants have reached at least Week 26, based on RECIST 1.1. ORR will be described as the overall number (%) of participants in each treatment arm with CR

Confidential Page 81 of 109

or PR and will be presented along with the respective 95% confidence intervals (CI) for each arm. For Arm 1, the primary analysis will include participant response prior to anti-PD-1 re-challenge (eg, before crossover to Arm 2). ORR by treatment stratum and lerapolturev dosing schedule will be conducted, as will other pre-determined subgroups defined in the SAP.

Additional secondary endpoints, including DOR, DRR, DCR, PFS and OS will also be summarized. DRR will be presented as the number (%) of participants with CR or PR lasting ≥6 months, along with 95% CI. DCR will be shown as the number (%) of participants with SD, PR, or CR together with the 95% CI. DOR, PFS and OS will be described using the Kaplan-Meier method. Additional details will be included in the SAP.

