3.3. TIMING OF ANALYSES

The final analysis will be completed after the last participant completes or discontinues the study and the resulting clinical database has been cleaned, quality checked, and locked.

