5.6. EFFICACY

5.6.1. Primary Efficacy Endpoints

The primary efficacy endpoint is ORR which is the overall number and percentage of participants in each treatment arm with confirmed CR or confirmed PR. The primary analysis for the safety run-in and Arm 1 will include participant response prior to crossover to Arm 2. ORR will be analyzed by treatment arm, dosing schedule and overall.

CONFIDENTIAL Page 26 19 November 2024

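### ORR has no response window in the SAP, but Arm 1 response is cut at a crossover that opens at Week 26, so the side-by-side arm ORRs cover unequal periods and tend to favour Arm 2

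*SAP*

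**What the plan says.** **Endpoint.** SAP 5.6.1 takes ORR as the "overall number and percentage of participants in each treatment arm with confirmed CR or confirmed PR". The SAP definitions (3.2.6), the estimand (5.6.1.1) and the primary analysis (5.6.1.2) add no time horizon. SAP 3.3 provides for a single analysis: "The final analysis will be completed after the last participant completes or discontinues the study". The protocol synopsis puts study duration at about 104 weeks.

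**Cut at crossover.** SAP 5.6.1 adds: "The primary analysis for the safety run-in and Arm 1 will include participant response prior to crossover to Arm 2". Protocol 8.5.1 has the same rule for Arm 1. Protocol 3.1.1 allows crossover on progression, on a PR of at least 6 months, or for participants who "have not had progression or confirmed partial response per RECIST v1.1 by week 26 on study".

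**Week 26 in the protocol.** Three places differ:
- The synopsis (Criteria for Assessments) refers to "participants achieving objective response (along with associated durations) or disease control by Week 26 or upon anti-PD-1 re-challenge".
- Section 2.1 defines ORR without a window: "the proportion of participants achieving confirmed complete (CR) or partial response (PR), per RECIST 1.1 criteria".
- Section 8.5.1 speaks of "ORR, which will be evaluated once participants have reached at least Week 26, based on RECIST 1.1".

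SAP section 7, which lists changes to planned analyses, does not mention the response window.

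**Arm comparison.** Protocol 8.3 plans comparisons such as Arm 1 versus Arm 2 without formal testing. SAP Table 14.2.1.1 summarises best overall response, and SAP section 5 has every summary table presented by treatment group.

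**The concern.** A participant who is stable at Week 26 could still become a late responder. In Arm 2 that participant stays under observation for the primary endpoint, and a response first seen at Week 36 or 48 counts. In Arm 1 the same participant may cross over at Week 26. From then on scans belong to the combination: SAP 4.2 assigns each assessment to the treatment at that time, and Protocol 8.5.4 resets the response baseline at crossover. A late response that monotherapy would have produced is then lost to Arm 1.

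The bias runs one way and would be there even if anti-PD-1 added nothing. A reader of Table 14.2.1.1 would see two ORRs in adjacent columns with nothing to show that they were observed for different lengths of time. In a trial randomised between monotherapy and combination, that contrast is the natural one to draw. The unresolved Week 26 wording makes matters worse, because the reader cannot tell which period either ORR is meant to cover.

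**Working it through.** **1. The plan's own figure.** The exact (Clopper-Pearson) 95% limits for x of n are the 2.5% quantile of Beta(x, n−x+1) and the 97.5% quantile of Beta(x+1, n−x).
- 5/15: 11.8% to 61.6%, as stated in SAP 3.1 and Protocol 8.3.
- 4/15: 7.8% to 55.1%, so 5 is the smallest count with a lower limit above 10%.
- P(at least 5 of 15) is 0.013 at a true rate of 10% and 0.596 at one third.

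Only Arm 2 QW participants enter this rule. Arm 1 follow-up does not appear in it.

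**2. Observation periods.** Imaging is at 6 and 12 weeks, then every 12 weeks (schedule of assessments).
- Scans up to Week 26: Weeks 6, 12 and 24. There is no scan at Week 26 itself.
- Later scans within 104 weeks: Weeks 36, 48, 60, 72, 84 and 96.
- Arm 2 non-progressor: all of these can contribute while the participant remains under assessment.
- Arm 1 non-progressor who crosses over at Week 26: only Weeks 6, 12 and 24.
- Arm 1 non-progressor who stays on monotherapy: the same as Arm 2.

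**3. Confirmation.** A response first seen at Week 24 has its next scheduled scan at Week 36. Until it is confirmed, an Arm 1 participant still meets the Week 26 criterion; the synopsis expressly includes unconfirmed PR or CR. After crossover, the confirming scan falls under the combination. An identical Arm 2 participant is confirmed at Week 36 and counted.

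**4. Illustrative size.** The documents give no late-response rate for this regimen. Protocol 1.1 quotes a median time to response of 2 to 3 months for anti-PD-1 in general. *Assume* exponential time to response with that median m. With 24 weeks = 24 × 7 / 30.44 = 5.52 months, the share after week t is S(t) = 2^(−t/m):
- After Week 24: 2^(−5.52/2) = 0.148 to 2^(−5.52/3) = 0.279.
- After Week 12 (2.76 months): 2^(−2.76/2) = 0.384 to 2^(−2.76/3) = 0.528.

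Let both arms have the same true ORR p = 1/3, and let c be the fraction of Arm 1's would-be late responders who cross over first. The spurious gap is p × S × c.

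| Responses lost to Arm 1 | c = 0 | c = 0.5 | c = 1 |
|---|---|---|---|
| First seen after Week 24 (S = 0.148 to 0.279) | 0 | 2.5 to 4.7 points | 4.9 to 9.3 points |
| Also those first seen at Week 24 and unconfirmed (S = 0.384 to 0.528) | 0 | 6.4 to 8.8 points | 12.8 to 17.6 points |

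With 15 per arm, the first row at c = 1 is 0.7 to 1.4 responders. The second row is an upper limit, since someone with an unconfirmed response may well stay on monotherapy.

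**5. What a Week 26 window would do to the activity rule.** With a true any-time ORR of 1/3 and a late share of 15% or 28%, the by-Week-26 rates are 0.333 × 0.85 = 0.283 and 0.333 × 0.72 = 0.240. P(at least 5 of 15) falls from 0.60 to 0.43 or 0.28.

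**The case against.** **The SAP follows the protocol's formal definition.** This stands. Section 2.1 has no window, and Section 8.5.1 sets a minimum follow-up that an end-of-study analysis satisfies. One synopsis sentence alone suggests a cut-off, and that sentence mixes response, disease control and re-challenge. A reader might infer that the protocol fixed ORR at Week 26 and the SAP dropped it. The documents do not support that. The protocol is inconsistent, and the SAP, which supersedes its statistical text (Protocol 8.5), does not resolve it.

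**The decision rule is unaffected.** This also stands as regards Arm 1. A reader might go further and say that late Arm 2 responses make 5 of 15 too easy to reach. One late responder can indeed turn 4/15 into 5/15. But the 10% benchmark is stated without a window, so counting late responses inflates the error only if 10% is meant as a by-Week-26 rate, which neither document says.

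**Crossover is optional.** This stands, and it limits the size: Arm 1 non-progressors who remain on monotherapy keep accruing. It does not remove the direction of the bias.

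**Cutting Arm 1 at crossover is right, and the comparison is untested.** The cut is reasonable for a monotherapy ORR. But a descriptive comparison is still planned, and it should compare like with like.

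**Conclusion.** The concern holds as a point about comparability and clarity. As written, the plan yields Arm 1 and Arm 2 ORRs over unequal periods, with a lean toward Arm 2 that grows with the proportion of Arm 1 non-progressors who cross over. The size cannot be derived from the documents. Under the stated exponential assumption and a common ORR of one third, it runs from zero (no crossover) to about 5 to 9 points (full crossover). It is larger if Week 24 responses also go unconfirmed because of crossover.

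The structure itself needs no assumption: it follows from the crossover rule, the imaging schedule and the end-of-study analysis. That responses are counted to study end is inferred from the SAP's silence on a window together with its section 3.3.

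The point does not show an inflated error rate for the 5-of-15 rule, nor a need to make Week 26 the primary definition. The last step of the working shows what that would cost in power.

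**What to change.** 1. **SAP 5.6.1 and 3.1:** state that ORR for the 5-of-15 rule is best confirmed response up to the final analysis, with Arm 1 and the run-in cut at crossover.
2. **Table 14.2.1.1:** add a common-window row with Clopper-Pearson limits in every group. Count responses both documented and confirmed by the Week 26 assessment (in practice the Week 24 scan) and before crossover. Requiring confirmation inside the window keeps a Week 24 response confirmed only at Week 36 from bringing the asymmetry back.
3. **Arm descriptions:** use that row for any Arm 1 versus Arm 2 statement, and footnote the any-time ORR as not comparable between arms.
4. **Reconcile the Week 26 wording** in the protocol synopsis, 2.1 and 8.5.1, and record the outcome in SAP section 7.
5. **Reconcile the crossover week.** Protocol 3.1.1, SAP 1.1 and SAP Table 3 footnote 13 give 26 weeks. SAP Table 2 footnote 13, in the schedule that covers monotherapy, gives 36. The week determines when the Arm 1 window can close.

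**Cost:** a few sentences and one table row. The common-window ORR will be lower. On scheduled scans it misses responses first seen at Week 24, so under the exponential assumption it would omit 38% to 53% of all responses, less where an unscheduled scan or caliper measurement confirms earlier. It should therefore serve as the comparable row and not as the headline ORR.

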5.6.1.1. Statement of Estimand

The **population for the trial** is defined through appropriate inclusion/exclusion criteria to reflect the targeted participant population for approval. The analysis population is based on the efficacy population.

The **treatments** of interest are lerapolturev alone or lerapolturev + an FDA-approved anti-PD-1 therapy by dosing schedule.

The **variable** of interest for ORR is the binary response value for a participant.

The ability to evaluate treatment effect using the variables may be impacted by **intercurrent events** (ICEs). Death and use of additional cancer treatments may all impact the interpretation of treatment effect. For ORR, a composite strategy will be used to address intercurrent events (ICEs) of potential death, and start of additional cancer treatments, meaning occurrence of any of these events prior to a participant achieving CR or PR will mean the participant is considered a non-responder.

The **population level summary measures** are the ORR and associated confidence intervals in each treatment arm and lerapolturev dosing schedule.

5.6.1.2. Primary Efficacy Analysis

The number of participants in each category of best overall response per RECIST v1.1 (confirmed CR, confirmed PR, SD, unconfirmed CR, unconfirmed PR, PD, non-evaluable (NE)) and ORR along with the associated exact 95% two-sided CIs using Clopper Pearson method will be computed within each treatment group and dosing schedule. A participants BOR will be determined based on Table 4.

Supportive data listings will also be provided.

Table 4 Best Overall Response When Confirmation of CR and PR are Required

First Timepoint	Second Timepoint	
Response	Response	Best overall response for ORR
CR	CR	CR
CR	PR	SD, PD or PR ^a
CR	SD	SD
CR	PD	SD
CR	NE or NA	SD
PR	CR	PR
PR	PR	PR
PR	SD	SD
PR	PD	SD
PR	NE or NA	SD
NE CD L	NE	NE

CR = complete response, PR = partial response, SD = stable disease, PD = progressive disease, and NE = not evaluable. a If a CR is truly met at first time point, then any disease seen at a subsequent time point, even disease meeting PR criteria relative to baseline, makes the disease PD at that point (since disease must have reappeared after CR). However, sometimes "CR" may be claimed when subsequent scans suggest small lesions were likely still present and in fact the patient had PR, not CR at the first time point. Under these circumstances, the original CR should be changed to PR and the best response is PR.

5.6.2. Secondary Efficacy Endpoints

The secondary efficacy endpoints for the study are:

- OS
- PFS by RECIST v1.1
- DOR by RECIST v1.1
- DCR by RECIST v1.1
- DCR-6mo by RECIST v1.1
- DRR by RECIST v1.1

5.6.2.1. Secondary Efficacy Analysis

OS, PFS, and DOR will be summarized using Kaplan-Meier method to estimate the median, 25% and 75% percentiles along with their 95% CIs. OS, PFS and DOR survival curve will be estimated using Kaplan-Meier method. PFS and DOR will use RECIST v1.1 definitions for response and progression of disease.

DRR will be presented as the number and percentage of participants with confirmed CR or confirmed PR (by RECIST v1.1) lasting \geq 6 months along with the 95% CI.

Analysis of DCR and DCR-6mo will be summarized. The associated exact 95% two-sided CIs using Clopper Pearson method will be computed within each treatment group and dosing schedule. DCR and DCR-6mos will use RECIST v1.1 definitions for response and SD.

5.6.3. Translational Analysis

Summaries of translational data are not covered by this SAP.

5.7. SAFETY

Participants receiving at least one lerapolturev injection will be analyzed for safety. Values for all safety variables will be listed by participant and visit (as applicable). Safety summaries by visit will use scheduled visits up to 30 days after the last dose of study drugs.

If a participant crosses over from monotherapy to combination therapy, then the treatment analyzed will be based on the treatment for that participant at the time of the assessment.

5.7.1. Adverse Events

AE will be mapped to a MedDRA version 24.0 by SOC and PT. If a participant experiences multiple events that map to a single PT, the greatest severity and strongest assessment of relation to a study drug will be assigned to the PT for the appropriate summaries. AE severity will be assessed according to the NCI CTCAE version 5. If CTCAE grading does not exist for an AE, the severity of the AE will be graded as mild (1), moderate (2), severe (3), life-threatening (4), or death (5).

AESIs will be identified within the EDC by the investigator.

The number of participants for the following groups will be summarized by treatment group and overall:

- Any TEAE
- Any TEAE related to
 - o lerapolturev

- o anti-PD-1 therapy
- Any TESAE
- Any TESAE related to
 - o lerapolturev
 - o anti-PD-1 therapy
- Any treatment-emergent lerapolturev AESIs
- Any treatment-emergent irAEs
- Any TEAE with CTCAE grade ≥ 3
- Any TEAE related to
 - o lerapolturev with CTCAE grade ≥ 3
 - o anti-PD1 therapy with CTCAE grade ≥ 3
- Any Grade 5 TEAE
- Any Grade 5 TEAE related to lerapolturev or anti-PD1 therapy

The occurrence of TEAEs and TEAEs related to lerapolturev, or anti-PD-1 therapy will be summarized by PT, SOC, and severity. Additionally, TEAEs will be summarized by PT in descending frequency. All AEs reported will be listed for individual participants showing both verbatim and PT. All AEs that occurred prior to initiation of study drugs will be excluded from the tables but will be included in the listings.

Adverse events occurring during screening due to lerapolturev-related procedures that are not standard of care (eg, PV booster) will be considered related to lerapolturev and summarized separately.

Additional analysis may be conducted to investigate rates of TEAE based on lerapolturev dose and/or schedule. Should there be a difference, we may perform additional analyses to discern whether there is a relationship between dose and occurrence of AEs.

Missing onset dates will be imputed as previously outlined in Section 3.2.3.2 as required to determine TEAE.

